9.2 Analysis principles

All the analysis will be conducted on an intention-to-treat basis unless otherwise specified. Only participants withdrawing from data collection will be excluded from the analysis. All hypothesis tests will be two-sided. No correction for multiple testing for secondary outcomes will be made but all secondary outcomes will be reported for transparency of the number of tests undertaken. All analyses will be adjusted for randomization minimisation variables and other names variables used in the primary analysis (pre-specified in the SAP) unless otherwise stated.

9.3 Missing data principles

9.3.1 Missing outcome data

The primary analysis will include all participants with known all-cause mortality outcome at 30 days. Significant missingness in mortality data is not expected as outcome data can be obtained from registries. The primary outcome variable will not be imputed in the main analysis.

9.3.2 Missing baseline data

We anticipate that missing baseline data will be minimal and attempts to collect missing baseline data will be made at the follow-up visits. Unknown factors of the medical history will be considered and entered to the CRF as "No". For missing baseline variables planned to be included in the main analysis models, if there are a reasonable proportion of participants with at least one missing value in order to avoid losing the participants from the models, values will be imputed using the mean value calculated from the non-missing values pooled data from both treatment arms. For categorical variables use of an indicator variable will be used [White 2005]

9.3.3 Missing troponin detection limits

It is possible that the lower detection limit will be missing for some of the troponin measurements. If the measurement is below the lower detection limit but the limit is missing for the given measurement, then it will be imputed in the following way:

- If the patient had a measurement before with an available lower detection limit, then we will impute the limit with last observation carried forward method assuming that the new measurement has most likely the same limit.
- Similarly, if the lower detection limit is missing and there aren't any limits from before but there is after then the first following available limit will be imputed.
- If none of the patient's measurements has available detection limits, then the most frequent limit of that centre will be imputed.

9.4 Subgroups

The impact of pre-specified sub-groups treatment efficacy will be investigated by including an interaction terms for sub-group variables with treatment arm in the model. This will be in the secondary analysis.

The following sub-groups will be explored through tests of interaction tests in the relevant model with interpretation of the p-value in terms of strength against the null hypothesis and as hypothesis generating, rather than using a binary threshold as it is likely these analysis will be under-powered.

- Sex
- Age
- Ethnicity
- Baseline troponin
- Baseline d-dimer

9.5 Patient flow (CONSORT diagram)

The patient flow (CONSORT diagram) is included in the protocol, and will follow recommendations of Moher et al 2001.

9.6 Baseline demographics

Baseline demographics and variables will be summarized as described by the general methodology section.

9.7 Phase I interim analysis

Interim analysis will include descriptive statistics of all outcome variables listed in 5.3, by arm. The primary efficacy analysis (as in section 9.8), safety analysis as outlined in section 9.10.

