5.3 Primary objective of internal pilot (Phase 1)

In order to ensure the study is a worthwhile undertaking and is safe we have included an internal pilot to assess the potential for bleeding harms.

The SAP was amended (version 2) to remove the assessment of efficacy from the objectives at the interim analysis. This change was made based on a blinded assessment of data completeness by the trial steering committee after recommendations were made by the data monitoring committee. Similarly, the effect on troponin and d-dimer were from the objectives of the interim analysis.

- To evaluate the harm profile of the combined treatment with a focus on bleeding outcomes.
- To assess the recruitment process and data collection quality.
- To check the control event rate included in the sample size calculation for Phase 2.
- To monitor adherence to the randomised arm (assessing the potential for contamination)

Internal pilot outcomes:

- Bleeding Academic Research Consortium (BARC) bleed at 30-days post randomization
- recruitment rate
- proportion of missing data for key outcomes
- control event rates

6 Design

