6.1 Study design

Parallel two arm randomized, single blind controlled trial with internal pilot.

C-19-ACS is a study determine if Acute Coronary Syndrome (ACS) is a major cause of mortality in patients with Novel Coronavirus 2 Related Disease (COVID-19) in patients. The study will randomize patients with confirmed COVID-19 in hospital to a 28-day course of standard ACS treatment to determine if the established ACS therapy has an impact on cardiovascular-outcomes.

The trial will include two phases: phase 1 and phase 2. Phase 1 will act as an integrated internal pilot with a close evaluation of safety, assessment of recruitment, contamination and quality of data collection. In phase 1, recruitment will include a minimum 170 patients of the total 3062

needed for the trial. The phase 1 analysis will occur after approximately 170 participants have 7 days follow-up information available. The result will be reviewed by an independent Data Monitoring Committee (DMC) who will make a recommendation to continue or halt the trial based on safety, or feasibility/quality issues. The DMC will also monitor the mortality event rate throughout the trial with the potential to recommend an increase to the sample size if it is assessed that increasing the precision of the treatment effect estimate will likely help inform subsequent policy treatment decisions through strengthening of evidence.

If there are no concerns at the end of phase I assessment, the trial will continue onto phase 2 in which a further approximately 30 sites will be recruited.

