6.2 Treatment groups

Patients will be randomized 1:1 ratio to the intervention group or control.

The intervention group will receive a combination of standard, evidence-based, therapies typically used for treatment of ACS. These are:

- If not already on Aspirin, Aspirin 75mg once daily PO (without a loading dose), unless contra-indicated
- If not already on clopidogrel or an equivalent anti-platelet agent, Clopidogrel 75mg once daily PO (without a loading dose), unless contra-indicated
- If not already on anti-coagulation, Rivaroxaban 2.5mg twice daily PO, unless contra-indicated.
- If not already on a statin, Atorvastatin 40mg once daily (evening) PO, unless contra-indicated
- If patient not already on a proton-pump inhibitor or equivalent, Omeprazole 20mg once daily PO, unless contra-indicated.

Previous or active use of any of the treatment medications will not be an exclusion to enrolment and randomization. Should, in the treating physician's option, there be any contra-indication to any single component of the ACS therapy, this single component will not be given, but other components will continue.

Should a patient in the arm randomized to the control group already be taking a component of the ACS therapy, this will be continued.

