9.10 Safety analysis

9.10.1 Bleeding Academic Research Consortium (BARC) bleed event at 30 days

The BARC bleed event at 30-days will be analysis using a proportional odds model, including the same baseline variables as the primary model. The aim of this model is to test if there is a significant difference in these ordinal outcomes and to estimate the magnitude of the difference. Results will be presented as odds ratios compared to the control group and their 95% confidence intervals.

9.10.2 Bleeding Academic Research Consortium (BARC) grade 3 to 5 bleed event at 30 days

This will be calculated in a similar way to the primary outcome.

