9.11 Interim analysis

The interim analysis will be performed after a minimum of 170 participants have been recruited and have a minimum of 7 days follow-up. The DMC will be responsible for reviewing all the data and advising on whether the trial should continue.

The following outcomes will be summarized by arm and compared between arm by calculating odds ratios, incidence rate ratios for count outcomes, or differences in mean. Safety summary statistics and between arm comparisons will be tabulated. Differences will be presented with 95% confidence intervals and p values, but the p-values will be interpreted in terms of strength of evidence using the continuous scale and not based on a binary threshold (e.g. 0.05).

- Bleeding Academic Research Consortium (BARC) bleed at 30-days post randomization
- peak troponin within 7- and 30-days post randomization
- recruitment rate
- proportion of missing data for troponin and mortality where due.
- Control event rates

A Kaplan Meier estimate for survival will also be presented with 95% CI around the curves

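### Phase 1 bleeding look: the adjusted models of section 9.10 are ill-suited to about 85 patients per arm, and no absolute risk difference or sparse-data method is named

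*SAP*

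**What the plan says.** Section 5.3 lists as the first aim of the internal pilot: "To evaluate the harm profile of the combined treatment with a focus on bleeding outcomes". Section 6.1 has the DMC "make a recommendation to continue or halt the trial based on safety, or feasibility/quality issues", and adds: "If there are no concerns at the end of phase I assessment, the trial will continue onto phase 2". On timing, section 9.11 states: "The interim analysis will be performed after a minimum of 170 participants have been recruited and have a minimum of 7 days follow-up".

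For the analysis at that look, section 9.7 asks for by-arm descriptive statistics of the outcomes in 5.3, and then "The primary efficacy analysis (as in section 9.8), safety analysis as outlined in section 9.10". Section 9.10.1 analyses BARC bleeding at 30 days with a proportional odds model carrying the primary model's baseline variables. Section 9.10.2 says of BARC 3 to 5: "This will be calculated in a similar way to the primary outcome". Under section 9.8 that is a mixed logistic model with age, sex, diabetes, coronary disease, hypertension, heart failure, the Appendix A troponin terms and a random site effect. Unadjusted and adjusted odds ratios are both reported, and the adjusted one is primary.

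Section 9.11 adds by-arm summaries and between-arm comparisons, by odds ratio for binary outcomes. "Differences will be presented with 95% confidence intervals and p values", with the p-values read on a continuous scale rather than against a threshold. Neither section names a method for sparse events or an absolute risk difference for bleeding.

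**The concern.** The 9.10 models are designed for the final analysis of about 3,000 patients. Section 9.7 applies them unchanged to a look with about 85 patients per arm, where bleeds may be counted in single figures. Two problems follow. First, the number of model terms approaches or exceeds the number of events. Second, if every bleed falls in the active arm, the odds ratio has no finite maximum-likelihood value, so the specified effect measure breaks down in a pattern that should point to harm.

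Bleeding is the stated focus of phase 1, and the look informs whether up to 3,062 − 170 = 2,892 further patients are randomised. The DMC should have an effect measure that works with the counts it is likely to see and that shows how large an excess remains possible.

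**Working it through.** **Inputs.** At least 170 patients with at least 7 days of follow-up (6.1, 9.11). For allocation, section 6.2 states: "Patients will be randomized 1:1 ratio to the intervention group or control". This gives 170 / 2 = 85 per arm. Tests are two-sided (9.2). The SAP gives no bleeding rate, so control rates of 1% to 10% are assumed below.

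**The plan's own figure.** The only sample size stated is for mortality, and it reproduces. For 25% v 20%, two-sided 5% and 90% power, the requirement is 1,464 per arm (1,504 with continuity correction), consistent with 3,000 in total. 3,000 / 0.98 = 3,061.2, which rounds up to 3,062. There is no corresponding figure for the bleeding look.

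**Terms against events.** The fixed effects are treatment, age, sex, diabetes, coronary disease, hypertension and heart failure (7), a three-knot spline for log troponin (2) and at least one detection-level term (1). That is about 10, plus site. At 5% v 10% the expected number of bleeds is 85 × (0.05 + 0.10) = 12.75. At 2% v 4% it is 5.1.

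**No control bleeds.** The probability is (1 − p)^85: 0.99^85 = 0.426 and 0.98^85 = 0.180.

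**Detection.** Exact binomial enumeration at 85 per arm, counting Fisher two-sided p < 0.05 with the excess in the active arm. The 5% level is only a yardstick.

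| Assumed control rate | No control bleeds | Doubling detected | Tripling detected |
|---|---|---|---|
| 1% | 43% | 0.3% | 2% |
| 2% | 18% | 3% | 13% |
| 3% | 7.5% | 7% | 26% |
| 5% | 1.3% | 16% | 51% |
| 8% | 0.1% | 29% | 78% |
| 10% | <0.1% | 37% | 89% |

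**Example, 6 v 0 bleeds.** An unadjusted maximum-likelihood logistic fit stops at a log odds ratio of about 22 with a standard error of about 14,000, so there is no finite estimate. On the same data Fisher's test gives p = 0.029. The risk difference is 6/85 = 7.1 points. The Wilson limits are 3.3% to 14.6% (active) and 0% to 4.3% (control). The Newcombe limits are:

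- lower: 7.1 − √[(7.1 − 3.3)² + 4.3²] = 1.3 points
- upper: 7.1 + (14.6 − 7.1) = 14.6 points

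**Example, 2 v 2 bleeds.** Each arm is at 2.35% with Wilson limits 0.65% to 8.18%. The Newcombe upper limit for the excess is √[(8.18 − 2.35)² + (2.35 − 0.65)²] = 6.1 points.

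**The case against.** The strongest reply is that the DMC does not depend on the 9.10 models. Section 9.7 itself requires by-arm descriptive statistics, 9.11 requires by-arm summaries and 95% intervals, and the DMC reviews all the data. A 6 v 0 split would be visible as counts. This stands. A reader might infer that the pilot would overlook its clearest harm signal, and the text does not support that. What fails is the between-arm estimate, not sight of the data.

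Four further objections also stand:

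- Section 9.11 rejects a p-value threshold, so missing an effect at 5% describes how little information 85 per arm carries. It does not describe a decision the SAP would take.
- A reader might infer that a tripling would usually be missed whatever the bleeding rate. It would not: detection is about even at 5% and 89% at 10%, and 170 is a minimum.
- Covariate adjustment is not what makes the odds ratio infinite. At 1% v 6%, for example, the chance of no control bleeds with at least one active bleed is 0.99^85 × (1 − 0.94^85) = 42%, and the unadjusted odds ratio fails equally in those cases.
- A p-value near 1 for 6 v 0 arises only with Wald inference, which the SAP does not specify. The likelihood-ratio test gives p = 0.003.

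It is also tempting to fault the SAP for setting no numerical bound on harm. That is a matter for DMC judgement, and such criteria are commonly kept in the protocol or a charter, neither of which is shown.

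The objections leave one gap open. The SAP fixes the model for this look, the measure it names for binary outcomes is the odds ratio, and it provides no absolute difference or sparse-data method.

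**Conclusion.** The point holds in a limited form. Section 9.7 sends the phase 1 bleeding comparison to models that are unstable with few events and give no finite odds ratio when the control arm has no bleeds: 43% likely at an assumed 1% control rate, 18% at 2%, and about 1% at 5%. The problem therefore matters most for uncommon outcomes such as BARC 3 to 5. Independently of the model, 85 per arm is imprecise. A doubling would usually not reach the 5% yardstick at control rates of 1% to 10%, and a tripling would usually not reach it only below about 5%.

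All rates are assumptions. The outcome is defined at 30 days but only 7 days of follow-up are required, so event counts at the look may be lower than computed here. The documents do not show that the DMC would be left without usable information, or that continuing the trial is tied to a non-significant result.

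**What to change.** In sections 9.7 and 9.11, for the phase 1 look only, replace the reference to the 9.10 models with:

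- counts by BARC grade and arm;
- the unadjusted risk difference for any BARC bleed and for BARC 3 to 5, each with a Newcombe or Miettinen-Nurminen 95% interval, and the upper limit shown to the DMC;
- an exact or mid-p test, or a Firth odds ratio.

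Keep the adjusted models of 9.10 for the final analysis.

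The change needs SAP wording and a simpler DMC table, and no new data. It adds no patients, so it does not remedy the low precision but makes it visible. The downside is that the phase 1 report will show openly that a sizeable excess is not excluded, for example up to 6.1 points with 2 v 2 bleeds.

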9.8 Primary efficacy analysis - All-cause mortality at 30-days post randomization

The primary outcome is all-cause mortality at 30-days post randomization. We will test the hypothesis that there is no difference in the odds of the primary outcome between the control and intervention groups using a mixed logistic regression model. The model will include the factors used for minimization and/or stratification (age, presence of diabetes, presence of coronary artery disease, and sex as fixed effects; and site as a random effect) and the following additional factors: (baseline log troponin level (as outlined in Appendix A), hypertension, and known heart failure). Both unadjusted (**Error! Reference source not found.**) and adjusted Odds Ratios (OR) and their 95% Confidence Interval (CI) will be presented but the adjusted results will be considered primary (Table 1: Adjusted results).

Observed mortality rate at 30-days post randomization will be tabulated for each arm (Table 1) with Kaplan-Meier survival curves presented.

9.8.1 Supplementary analysis to the primary analysis 1

A Bayesian analysis will also be undertaken using uninformative prior distributions using a logistic regression model. This analysis will be undertaken to provide an alternative interpretation of the treatment effect in terms of the posterior probability of the treatment strategy being superior to standard treatment.

9.8.2 Supplementary analysis to the primary analysis 2

A complier average causal effect (CACE) analysis will also be performed to estimate the effect of the treatment strategy when adhered to as planned in the protocol for the active arm.

Compliance in the active arm will be defined as participants who received at least 50% of the planned dose (whilst alive) for the treatments they would have been eligible for at the time of randomisation. The complier average causal effect will be estimated by a two-stage least squares instrumental variable regression. Randomisation is taken to be the instrumental variable for treatment received and there will be adjustment for the fixed effect variables used in the primary model. Analysis will be undertaken using the Stata using “ivregress 2sls” command or equivalent.

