8.1 Baseline and demographic variables

The following baseline variables will be captured with measures of centrality and distribution reported:

- Age
 - Age > 60
- Sex
- Ethnicity
- Past medical history
 - Hypertension
 - Diabetes
 - Known coronary artery disease
- Medication use
 - Aspirin
 - Clopidogrel.
 - Other anti-platelet agents.
 - Oral anticoagulant
 - Direct oral anticoagulant usage
 - Usage of prophylactic dose low-molecular weight heparin
 - Usage of treatment dose low-molecular weight heparin
 - Statin
 - Proton pump inhibitors
- Biomarkers
 - Haemoglobin
 - C-reactive Protein (CRP)
 - D-dimer
 - Troponin
- Hospital admission
 - Time from symptoms to admission
 - Time from admission to randomization
- Site

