9.9.4 Discharge from hospital (length of stay)

Discharge from hospital will be analysed using Cox proportional hazard models to test the hypothesis that there is no difference in this between the control and intervention groups.

Kaplan-Meier survival curves, median length of hospital stay, and the log-rank test result will also be presented. Both adjusted (age, sex, baseline troponin level, hypertension, diabetes, heart failure) and unadjusted Hazard Ratios (HR) and their 95% Confidence Interval (CI) will be presented. The adjusted results taken as primary. For Cox regression models the proportionality assumption will be assessed graphically (using diagnostic plots). If the assumption does not meet the median difference and the result of log rank test will be presented.

Both the length of stay from admission and length of stay from randomisation will be presented.

9.9.5 Binary outcomes (need for invasive ventilatory support, mechanical circulatory support, renal replacement therapy, ECMO)

Binary outcomes including:

- need for non-invasive ventilatory support
- need for invasive ventilatory support
- need for mechanical circulatory support
- need for renal replacement therapy

will be compared between the arms using logistic regression adjusting for the stratification factors and for variables included in the primary model. The aim of this model is to test if there is a significant difference in these binary outcomes and to estimate the magnitude of the difference. Results will be presented as odds ratios compared to the control group and their 95% confidence intervals.

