11 REFERENCES

12 Appendix A: Statistical methods for including troponin level and lower detection limit in the model

Troponin assumed to be a strong predictor of the primary outcome thus it might be associated with the other outcomes as well. Troponin levels, both baseline and peak levels will be log transformed and panned to be added to the models using restricted cubic splines using the methods described by Frank Harrell [<https://discourse.datamethods.org/t/comparing-2-biomarkers-using-restricted-cubic-splines-how-to-interpretation-model-building/663/15>].

We assume a proportion of the measurements will be below the lower detection level. Additionally, the lower detection level could be different between the tests used even for the same patients. To overcome this issue four variables will be used:

- Troponin level: log transformed added as restricted cubic splines (*troponin*)
- Detection indicator variable 1: binary, 1 if there is an available measurement, 0 if measurement was taken but it is below the lower detection level (*detected₁*)
- Detection indicator variable 2: binary, 0 if there is an available measurement, 1 if measurement was taken but it is below the lower detection level (*detected₂*)
- Lower detection level: the threshold level of the given test, categorical or continuous depending on the number of different levels (*detection_level*)

These will be added to the model in the following way for both logistic regression and Cox models:

$$Outcome_i = Treatment_i + minimisation\ variables_i + detected_1 * rcs(\log\ troponin, 3) + detected_2 * detection\ level$$

This method will be used for both baseline and peak troponin levels (if used) depending on the aim of modelling.

The first interaction term (*detected₁ * detection_level*) as a non-zero value if there is a detected troponin and in this case the second interaction term is always zero.

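### The discharge Cox model leaves out two allocation factors without saying why, and the plan's handling of unknown history and of heart failure as a covariate is inconsistent

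*SAP*

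**What the plan says.** **Allocation (SAP 6.8).** Minimisation runs over age above 60, diabetes, coronary artery disease and sex, stratified by recruitment site.

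**Primary model (9.8).** The allocation factors enter as "age, presence of diabetes, presence of coronary artery disease, and sex as fixed effects; and site as a random effect". The additional covariates are "baseline log troponin level (as outlined in Appendix A), hypertension, and known heart failure".

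**General rule (9.2).** "All analyses will be adjusted for randomization minimisation variables and other names variables used in the primary analysis". The sentence ends by allowing exceptions where the plan states otherwise.

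**Discharge (9.9.4).** The Cox model has its own list: "Both adjusted (age, sex, baseline troponin level, hypertension, diabetes, heart failure) and unadjusted Hazard Ratios (HR"). The adjusted hazard ratio is the primary result for this outcome.

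**Captured variables (8.1).** The list opens with "The following baseline variables will be captured with measures of centrality and distribution reported". Under past medical history it has three entries: hypertension, diabetes and "Known coronary artery disease".

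**Unknown history (9.3.2).** "Unknown factors of the medical history will be considered and entered to the CRF as" 'No'. The same section then prescribes an indicator variable for missing categorical covariates.

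**The concern.** The covariates used for allocation should normally reappear in the analysis. Minimisation and stratification make the arms more alike on those factors than chance would. A model that ignores them computes its standard error as if that balance had not been imposed. In a Cox model, leaving out a balanced prognostic factor also tends to pull the hazard ratio towards 1. Site deserves particular attention here, because discharge practice can differ between hospitals and phase 2 is to add about 30 sites.

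The 'No' coding is a separate matter. It classes a patient whose history is unknown as free of the condition, and does so on the CRF, so the missingness cannot be seen later in the data. It can reach diabetes, coronary disease, hypertension and heart failure, which are all the history covariates in the primary model. Two of them are minimisation factors.

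The heart failure mismatch matters because the adjusted result is the primary one, so every term in it should be traceable to a listed baseline variable.

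**Working it through.** **1. The plan's own figure.** The sample size is not in question; it was reproduced for completeness. With 25% v 20%, two-sided 5% and 90% power, the pooled formula gives, per arm,

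n = [1.960·√(2·0.225·0.775) + 1.282·√(0.25·0.75 + 0.20·0.80)]² / 0.05² = 1464,

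or 2928 in total. With a continuity correction it is 1504 per arm, 3008 in total. Both are close to the stated 3000, and 3000/0.98 = 3061.2, rounded up to 3062, as in 6.6.1.

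**2. Covariate lists side by side.**

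| Term | Allocation (6.8) | Primary model (9.8) | Discharge Cox (9.9.4) | Listed in 8.1 |
|---|---|---|---|---|
| Age | yes | yes | yes | yes |
| Sex | yes | yes | yes | yes |
| Diabetes | yes | yes | yes | yes |
| Coronary artery disease | yes | yes | **no** | yes |
| Site | yes (stratification) | yes (random) | **no** | yes |
| Baseline troponin | – | yes | yes | yes |
| Hypertension | – | yes | yes | yes |
| Heart failure | – | yes | yes | **no** |

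The only primary-model terms missing from the Cox list are coronary artery disease and site, and both are allocation factors. The only primary-model term missing from 8.1 is heart failure. The ordinal model in 9.9.1 also writes its own list, but keeps all five allocation factors; what it leaves out is troponin, hypertension and heart failure.

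**3. Unknown history.** Once an unknown item has been entered as 'No', the field is complete. An indicator equal to 1 for missing values is then 0 for every such patient. For these items the second rule of 9.3.2 has nothing to act on.

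**4. Does the 'No' coding shift the primary treatment effect?** The SAP gives no heart failure prevalence or prognostic effect, so the following are assumptions: prevalence 10%, odds ratio for death 2, N = 3000, and true treatment odds ratio (0.20/0.80)/(0.25/0.75) = 0.75. A given share of heart failure cases was recoded to 'No' in both arms, with 400 simulated trials per row.

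| Heart failure cases coded 'No' | Treatment OR | Mean SE of log OR |
|---|---|---|
| 0% | 0.748 | 0.0882 |
| 10% | 0.750 | 0.0881 |
| 30% | 0.746 | 0.0880 |
| 50% | 0.749 | 0.0879 |
| 100% (term drops out) | 0.749 | 0.0878 |

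The simulation error of each mean log odds ratio is about 0.088/√400 = 0.0044. The widest gap between rows, ln(0.750/0.746) = 0.005, is therefore within noise.

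**5. Not computed.** The precision lost in the discharge model cannot be sized from the document. It depends on how strongly coronary disease and site predict discharge, and the SAP gives neither.

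**The case against.** **The exception in 9.2.** A reader might infer that 9.2 strictly requires coronary disease and site in the Cox model. It does not: the rule yields where a section says otherwise, and 9.9.4 gives its own list. This part of the objection stands. What remains is an unexplained departure in which every other primary-model term is kept and only two allocation factors go, which looks like an oversight.

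**The CRF is not shown.** A reader might infer that the primary model cannot be fitted because heart failure is not collected. The document does not establish that. It shows only an omission from 8.1, and 9.1 plans medical-history summaries coded with MedDRA, which may mean a wider history is recorded.

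**Unknown is not the same as missing.** An answer of unknown and an empty field can be different things, so the two rules in 9.3.2 could coexist. That is fair, but the section does not draw the distinction, and calling unknown 'No' is still misclassification. It is also fair that minimisation needs a definite value for diabetes and coronary disease; recoding them afterwards would separate the model from the allocation data.

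**Appendix A.** Its formula omits hypertension, heart failure and site, so a reader might infer that it misstates the primary model. It is a schematic for coding troponin, introduced with "These will be added to the model in the following way for both logistic regression and Cox models", and 9.8 itself gives the full covariate set. A reader might also infer that the fit depends on troponin units. That needs a continuous detection level and an interaction without main effects. The appendix allows a categorical level and speaks of coefficients for the different levels. Even in the unfavourable reading, a simulation under assumed limits moved the treatment log odds ratio only between -0.281 and -0.283.

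**Conclusion.** The point holds as one of precision and consistency. The 9.9.4 list omits two allocation factors without a stated reason. The coding rule for unknown history disables the indicator rule beside it. One covariate of the primary model is missing from the list of captured variables. All three follow from the text alone.

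No material bias in the primary treatment effect is shown. The illustration supports that for a covariate with 10% prevalence and an odds ratio of 2, miscoded alike in both arms; it does not cover the discharge model. The primary model in 9.8 contains every allocation factor, so the standard-error concern is confined to the discharge outcome. The changes are worth making before unblinding, but they do not threaten the trial's main conclusion.

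**What to change.** 1. **9.9.4:** add coronary artery disease to the adjusted Cox model and account for site, either as strata or as a shared frailty. A frailty is closer to the random site effect in 9.8. Strata make no distributional assumption, but small sites contribute little. If the shorter list is intended, say so and give the reason.
2. **9.3.2:** record unknown history as unknown where this can still be recovered, and apply the indicator rule to it. For diabetes and coronary artery disease, keep the value used at minimisation as the model covariate. State whether unknown and missing are treated differently.
3. **8.1:** add known heart failure if it is on the CRF. If it is not, remove it from 9.8 and 9.9.4 before unblinding.

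The cost is mainly SAP wording. The one practical limit is that version 2 of the SAP followed a review of accumulated data, so some values already entered as 'No' may not be recoverable; the report should then say so.
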